4 TRIAL DESIGN

4.1 Description of Trial Design

This trial is a FIH, open-label, multicenter trial to evaluate the safety, tolerability, PK, pharmacodynamics, immunogenicity, and preliminary efficacy of GEN3009 (DuoHexaBody®-CD37) as a single agent and in combination with GEN3013 (DuoBody®-CD3xCD20, epcoritamab) in subjects with R/R B-cell NHL.

The trial will be conducted in 2 parts, Dose Escalation and Expansion. Up to 90 subjects with R/R B-cell NHL will be enrolled in the Dose Escalation, and approximately 92 subjects will be enrolled in the Expansion as follows:

- GEN3009 monotherapy cohorts: R/R DLBCL (N=20), R/R FL (N=20), and R/R CLL (N=20)
- GEN3009 + GEN3013 combination cohorts: safety run-in phase in R/R DLBCL or R/R FL (N=6-12) followed by Expansion phase in R/R DLBCL(N = 20).

For GEN3009 monotherapy cohorts , GEN3009 will be administered IV in 4-week cycles (ie, 28 days), with a schedule of weekly dosing in Cycles 1 through 3, every second week in Cycles 4 through 9, and every 4 weeks in Cycle 10 until disease progression, unacceptable toxicity, death or end of trial.

For GEN3009 + GEN3013 combination cohorts, GEN3009 will be administered IV in 4-week cycles (ie, 28 days), with a schedule of weekly dosing in Cycles 1 through 3, and every 4 weeks in Cycles 4 through 12 until up to a maximum of 12 cycles or any discontinuation criteria met (see Section 8), whichever occurs earlier. GEN3013 will be administered subcutaneously (s.c.) in Cycles 1 (starting from C1D8) through 3 , and then every 4 weeks in Cycles 4 through 12 until up to a maximum of 12 cycles or any discontinuation criteria met, whichever occurs earlier (see Table 21). After completion of Cycle 12, subjects who are in SD or better will have the option to continue receiving GEN3013 every 4 weeks until any discontinuation criterion is met.

Table 21 Dose and Schedule

GEN3009 IV as assigned	GEN3013 s.c.
DL1: CCI mg	DL1: 48 mg
DL2: RP2D	
• Cycles 1-3: Days 1, 8, 15, 22• Cycles 4-12: Day 1 
• Cycle 1:
◦ 0.16 mg (priming dose) on Day 8◦ 0.8 mg (intermediate dose) on Day 15◦ 48 mg (full dose) on Day 22• Cycles 2 and 3: 48 mg on Days 1, 8, 15, and 22• Cycles 4-12: 48 mg on Day 1 
After completion of Cycle 12:
 
• Subjects who are in SD, PR or CR:
◦ Every 4 weeks (Cycles 13, 14, 15+): 48 mg on Day 1

In treatment Cycle 1 during the Dose Escalation, all subjects are required to remain at the clinic after the GEN3009 administration for at least 4 hours where they will be observed for AEs, have vital signs measured, and have blood samples taken for laboratory parameters such as cytokines,

[figure not shown]
PK, and pharmacodynamic measurements. Observation of up to 24 hours postdose during Cycle 1 is permissible at the discretion of the investigator.

In treatment Cycle 1 during the Expansion, all subjects (including those in the combination cohort) are required to remain at the clinic after the GEN3009 administration for at least 2 hours where they will be observed for AEs and other assessments.

In the GEN3009 + GEN3013 combination cohort, all subjects must be hospitalized for CRS monitoring for at least 24 hours after the third dose (first full dose) of GEN3013 (ie, 48 mg) at Cycle 1 Day 22. Additional or longer hospitalization is based per the investigator's discretion.

The design of the GCT3009-01 trial is shown in [Figure 1](#).

Figure 1 GCT3009-01 Trial Design

4.1.1 Dose Escalation

The Dose Escalation will consist of 10 DLs (including one optional intermediate dose level) as shown in [Figure 1](#).

The initial 3 DLs will be single-subject cohorts, which is the accelerated titration part of the Dose Escalation. The start of standard titration begins with the enrollment of the 3-subject cohorts at the fourth DL. Additional intermediate dose levels (eg, CCI mg) may also be explored based upon emerging data.

In the accelerated titration part of Dose Escalation, single-subject cohorts will be expanded to a 3-subject cohort if the subject experiences a grade ≥ 2 toxicity (ie, related AE), during the DLT evaluation period (ie, 28 days), or based on the decision of the sponsor's SC. When those subjects have completed their DLT evaluation period, the escalation model in Section [4.1.1.1](#) will be

initiated. If any single-subject cohort is expanded to a total of 3 subjects, all subsequent cohorts will initially have 3 subjects per cohort.

After all subjects within a DL cohort have completed the DLT evaluation period, the DEC will review the data and propose for initiation of the next DL cohort. The sponsor's SC will have to endorse the proposal before the next DL cohort can start dosing subjects. To supplement routine safety monitoring by the SC, as outlined in this protocol, a DMC will monitor safety data for the trial on a quarterly basis or more frequently as determined by the sponsor. Recommendations from the DEC, SC, and DMC will be based on evaluation of all available data including but not limited to clinical, safety, PK and pharmacodynamic data. Additional details regarding DEC, SC, and the DMC can be found in Sections 10.8 and 10.9.

The timeframe for dosing subjects in a DL cohort should proceed as follows:

- For an investigated, non-cleared DL, there should be at least 3 days between administration of the first dose to the first subject and the second subject within the same DL.
- Any additional subjects dosed in the investigated, non-cleared DL should receive their first dose at least 1 day apart.
- For a DL cleared for safety as recommended by the DEC/SC, there is no specific timeframe for subjects to receive their first dose (ie, additional subjects may be treated in parallel at the respective DLs that are considered safe).

4.1.2 Expansion

Following the determination of the MTD/RP2D, the Expansion will recruit approximately 92 subjects in 4 parallel expansion cohorts (GEN3009 in R/R DLBCL [n=20], GEN3009 in R/R FL [n=20], GEN3009 in R/R CLL [n=20], and GEN3009 + GEN3013 in R/R DLBCL [n=20] with

a preceding safety run-in [$n = \sim 6-12$; R/R DLBCL or FL]) to provide additional safety and initial efficacy information, as well as more detailed data related to the MoA. Expansion cohorts will start and enroll in parallel and independently unless otherwise decided by the sponsor.

4.1.2.1 Safety Run-in for the GEN3009 + GEN3013 Combination Cohort

The safety run-in will be conducted to assess the initial safety and tolerability of escalating GEN3009 DLs in combination with GEN3013 RP2D prior to the initiation of the GEN3009 + GEN3013 DLBCL expansion cohort.

GEN3013 will be administered as s.c. injections at RP2D with a step-up dosing method (ie, priming dose followed by intermediate and full dose while GEN3009 monotherapy will be administered as IV infusions at assigned DL (ie, **CC1** mg [DL1] and RP2D from Dose Escalation part [DL2])). Only cleared DLs of GEN3009 monotherapy at Dose Escalation can be studied in combination with GEN3013.

Decision regarding dose escalation and de-escalation will follow the dose escalation/de-escalation rules specified in Section 4.1.1.1. For DLs with 3 DLT-evaluable subjects, the decision will be consistent with the “3+3” design, ie, escalate if no DLT is observed, enroll 3 additional subjects if 1 DLT is observed and de-escalate if 2 DLTs are observed. If 3 DLTs are observed, the DL will be terminated. For DLs with 4 or more DLT-evaluable subjects the decision will be based on the rules of mBOIN design.

Dosing of subjects will be staggered following the same rules described in Section 4.1.1.

One combination treatment cycle will be 28 days. DLTs (see Section 7.3) will be evaluated during the first 28 days. After completion of the DLT period, based on cumulative safety data and the recommendation from the dose decision criteria described above, the DEC will provide a recommendation on the respective DL to the SC. The SC must endorse using the recommended or higher dose prior to implementation. Refer to Section 4.1.1.1 for further information including, but not limited to, mBOIN design and MTD/RP2D definitions.

4.2 Trial Design Rationale

This trial is being conducted to identify the MTD and/or RP2D of GEN3009, evaluate safety, and obtain preliminary efficacy of GEN3009 as a single agent and in combination with GEN3013 in subjects with R/R B-cell NHL, including CLL.

Escalation and de-escalation in the Dose Escalation and combination safety run-in cohorts will be guided by the mBOIN approach. To collect further data on the safety, tolerability, PK and anti-lymphoma activity, the selected RP2D of GEN3009 from the Dose Escalation will be studied in the Expansion. The Expansion will include 4 cohorts (ie, R/R DLBCL, R/R FL and R/R CLL in monotherapy cohorts, and R/R DLBCL in the GEN3009 + GEN3013 cohort with a preceding safety run-in) for further investigation. A safety run-in for the combination cohort, evaluating escalating DLs of GEN3009 with GEN3013 for DLTs, will ensure the safety and tolerability of the GEN3009 + GEN3013 combination prior to the initiation of the combination expansion.

4.3 Dose and Schedule Rationale

4.3.1 GEN3009 Monotherapy Cohorts

A starting dose of █ mg of GEN3009 is proposed for this FIH clinical trial. This dose was derived by an integrated evaluation of preclinical pharmacology, PK, and toxicology studies.

A maximum recommended starting dose (MRSD) was defined using the HNSTD of 10 mg/kg in the pivotal GLP toxicity study as a starting point. A translational PK model based on cynomolgus monkey PK data was used to derive the human dose expected to give rise to 1-week average plasma exposure equivalent to one-sixth that in cynomolgus monkey at the HNSTD. The resulting dose of 2.34 mg/kg can be considered the MRSD.

GEN3009 was shown to have pharmacological activity at lower DLs. It showed significant effects on tumor size and inhibition of tumor outgrowth in various mouse xenograft models at 0.1 mg/kg. Furthermore, transient but substantial B-cell depletion was observed in cynomolgus monkey at 0.1 mg/kg. This pharmacological activity *in vivo* was compared to a minimum anticipated biological effect level (MABEL) approach based on CDC *in vitro* as an endpoint. CDC is expected to be the driving effector mechanism given that the DuoHexaBody format strongly enhances hexamer formation and C1q binding. The EC50 for CDC was established in a clinically relevant setting using *ex vivo* primary subject samples. The translational PK model was used to derive the dose expected to give rise to a 1-week average concentration equal to the CDC EC50 of 0.145 µg/mL, resulting in a dose of 0.25 mg/kg.

As a conservative approach, a FIH starting dose of █ CCI mg/kg was selected, which is expected to be at the lower end of the pharmacologically active range. The dose was converted to a flat dose equivalent of █ mg.

A high degree of receptor occupancy (ie, target saturation) throughout the dosing interval is often correlated with optimal anti-tumor activity of therapeutic antibodies with similar MoAs (CDC, ADCC, ADCP [eg, daratumumab and ofatumumab], etc). Therefore, maintaining a high % of CD37 saturation would be critical for efficacy. IgG1 Fc-domain associated effector functions including CDC, ADCC, and ADCP are known to require a high degree of receptor occupancy throughout the dosing interval for optimal effect. In cynomolgus monkey, approximately linear PK was observed at 3 mg/kg and above, suggesting sustained saturation of target mediated clearance. A near complete depletion of B cells in circulation was observed at these dose levels. In patients, the additional CD37 on malignant cells is expected to increase the dose required for sustained target saturation compared to healthy cynomolgus monkeys. Target mediated clearance is expected to be reduced over the course of treatment at efficacious dose levels due to the depletion of malignant cells, so that target saturation can be maintained with less frequent dosing. The schedule therefore starts with weekly dosing for the first 3 cycles of 28 days before the dosing frequency is reduced to once every 2 weeks (six 28-day cycles; Cycle 4 through 9) and once every 4 weeks (Cycle 10 and onwards).

Preliminary results from the Dose Escalation part of GCT3009-01 among patients treated with GEN3009 at doses ranging from █ mg to █ CCI mg at dose intervals of weekly in cycles 1-3, biweekly in cycles 4-9, and monthly from cycle 10 and beyond have shown the following:

- GEN3009 was well-tolerated with clinically manageable side effects at doses up to █ CCI mg. The most common TEAEs were IRRs and the most frequent laboratory

abnormalities were neutropenia. Both IRR and neutropenia are not dose-dependent; No dose-dependent toxicity has been observed so far.

- From the PK perspective, GEN3009 exhibited target-mediated drug disposition as expected, particularly at lower dose/concentration levels and resulting in rapid clearance of the drug-CD37 complex. High interindividual variability in target-mediated clearance was observed. For the majority of subjects doses up to **CCI** mg and for one out of three subjects at **CCI** mg were not sufficient to maintain saturating exposure throughout the dosing interval.

It is at present apparent that the highest dose initially planned of **CCI** mg is not sufficient to overcome target-mediated drug disposition in all subjects, and higher doses (eg, \geq **CCI** mg) are required to improve target saturation and minimize the impact of target-mediated clearance. Higher dose levels of GEN3009 (ie, **CCI** mg, **CCI** mg [optional intermediate dose], and **CCI** mg) are therefore added to the Dose Escalation to achieve target saturating exposure.

4.3.2 GEN3009 + GEN3013 Combination Cohort

The dosage of GEN3013 that will be tested in the combination regimens is the RP2D (ie, full dose of 48 mg) declared for R/R DLBCL and FL from the GCT3013-01 trial (NCT03625037). A step-up dosing schedule (ie, 0.16 mg on C1D8 [priming dose]; 0.80 mg on C1D15 [intermediate dose]; 48 mg on C1D22 [full dose]; and onward) for GEN3013 is selected to reduce the risk of CRS.

There will be 2 parts to test the GEN3009 + GEN3013 combination regimen:

- A safety run-in phase in R/R DLBCL and FL: to assess the safety, tolerability, PK, and immunogenicity of the GEN3009 + GEN3013 combination regimen. GEN3009 will be tested at 2 DLs: DL1 at **CCI** mg and DL2 at RP2D. GEN3013 will only be tested at a fixed DL at 48 mg.
- Expansion phase in R/R DLBCL: to assess the preliminary efficacy of the GEN3009 + GEN3013 combination regimen at the selected DL of GEN3009 from the safety run-in phase combined with GEN3013 at 48 mg. Safety, PK, and MRD will also be studied for the combination.

Starting with GEN3009 at **CCI** mg is considered to be appropriate based on the safety findings from subjects (N=18) treated with GEN3009 at up doses up to **CCI** mg. Specifically, IRRs observed with GEN3009 treatment were not dose-dependent and IRRs could be well managed. Laboratory abnormalities such as neutropenia were transient and neutrophil counts recovered within a few days. Granulocyte colony stimulating factor (G-CSF) administration at the onset of Grade 3 or Grade 4 neutropenia was sufficient for count recovery by the next dose.

Due to the non-overlapping MoAs for the individual study drugs (ie, GEN3009, GEN3013), it is deemed safe to start GEN3009 at **CCI** mg on C1D1 followed by the combination regimen from C1D8 and onward. The lead-in dose of GEN3009 can potentially reduce the risk of CRS with GEN3013.

It is hypothesized that a more robust (ie, deeper, earlier, and more durable) overall clinical benefit can be achieved with the GEN3009 + GEN3013 regimen. Target-mediated clearance of GEN3009 is expected to be reduced over the course of treatment given to the depletion of malignant cells as a result of a potentially deeper and earlier tumor response with the combination treatment, so that target saturation can be maintained with less frequent dosing. Thus, this trial will test a less frequent schedule of GEN3009 in the combination cohort as compared to the GEN3009

monotherapy cohorts (ie, every 4 weeks instead of q2w in Cycle 4 and onward, and a fixed duration of 12 months instead of continuous treatment until disease progression). Subjects who achieve SD or better at the completion of 12 months will have the option to receive GEN3013 until disease progression to maintain the clinical benefit based on the investigator's discretion.

4.4 End of Trial and End of Treatment Definitions

4.4.1 End of Trial

The trial is considered completed when the last subject dies or withdraws from the trial. However, the maximum trial duration is 5 years after the last subject's first treatment in the trial. Following trial termination, the sponsor will make their best effort to ensure provision of post-trial access to GEN3009 and/or GEN3013 for those ongoing trial subjects with a potential treatment benefit, in accordance with local laws and requirements.

4.4.2 Treatment Discontinuation

Treatment should continue until the subject fulfills 1 of the treatment discontinuation criteria (refer to Section [8.1](#)).

4.4.3 Trial Stopping Rules

If any of the events listed below occur, a prompt cumulative review of safety data will be conducted by the DMC to determine whether the trial should be discontinued permanently.

- Events outside of the DLT window, in the Dose Escalation part and in the expansion part of the trial, that in the judgment of the sponsor are deemed serious enough to warrant an immediate comprehensive evaluation by the SC;
- If at any time, all DLs are considered unsafe as defined by the mBOIN;
- Any safety finding assessed as related to GEN3009 and/or GEN3009 + GEN3013 combination treatment that, in the opinion of the DMC, contraindicates further dosing of trial subjects.

Any recommendation of the DMC must be approved by the sponsor SC.

In addition, to ensure subject safety, the following stopping criteria are applicable to subjects who have completed the DLT period during the Dose Escalation, as well as subjects enrolled in Expansion:

- $\geq 33\%$ of subjects experiencing Grade 3 or greater treatment-emergent IRRs, or
- $\geq 33\%$ of subjects experiencing Grade 4 neutropenia lasting >7 days not attributable to underlying disease, or
- $\geq 33\%$ of subjects experiencing Grade 3 or greater CRS or ICANS.

As noted in Section [10.8](#), the DMC will review the totality of the data and monitor safety for the trial on a quarterly basis or more frequently during the Dose Escalation and at pre-specified intervals during the Expansion (including safety run-in) as defined in the DMC charter.

For each individual subject who has already received GEN3009 or GEN3009 + GEN3013 combination and is currently in the trial at the time the trial stopping criteria are met, the benefit-risk whether to stop or continue treatment will be assessed. To allow continuation of treatment, DMC consultation will be considered. All subjects continuing GEN3009 or GEN3009 + GEN3013

combination after trial termination should continue to have investigator follow-up for safety until the subject's condition returns to baseline or until the start of a new anti-cancer therapy, whichever comes first.

Where applicable, regulatory authorities and independent ethics committees (IECs)/institutional review board (IRBs) will be notified of any significant actions taken with the trial.

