6.6 Concomitant Medications and Therapies

6.6.1 Permitted Concomitant Medications and Therapies

Investigators may prescribe concomitant medications or treatments deemed necessary to provide adequate supportive care except for those medications identified as "prohibited" (Section [6.6.2](#)).

The following concomitant medication and therapies are permitted during the trial:

- Local palliative radiotherapy on non-target lesions is allowed.
- G-CSF and other hematopoietic growth factors may be used in the management of acute toxicity, such as febrile neutropenia and neutropenia, when clinically indicated or at the investigator's discretion. In case of \geq Grade 3 neutropenia, use of growth factors is mandated in the Dose Escalation and Safety Run-in parts of the study.
- Blood cell transfusion is allowed if clinically indicated.
- Intravenous immunoglobulin (IVIg) is permitted, if clinically indicated.
- Multivitamins, vitamin D, calcium, and supplements in prevention of weight loss. Prescribed medicinal cannabinoids as palliative therapy are allowed.
- Anti-hypertensives are allowed as concomitant medications. However, due to the transient hypotension observed in the monkey toxicology study, consider withholding anti-hypertensive medication for 12 hours prior to infusions.

The sponsor's medical monitor/designee should be contacted if there are any questions regarding concomitant medication or prior therapy. Refer to Section [7.4.3](#) for additional guidance on permitted/required treatments for toxicity management.

The trial site will supply supportive medications, eg, premedication, anti-viral medication, anti IL-6R. Immediate access to tocilizumab is mandated on site.

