1.1 Preface

The objective of this document is to detail the statistical methodology to be used for the interim and final statistical analyses of the Dose Escalation part and the Dose Expansion part of study GCT3009-01.

This statistical analysis plan (SAP) covers the analysis of both parts of the trial and is based on the following information and documents:

Trial Protocol	16 Dec 2019; v 4.0 (Amendment 2)
Unique Case Report Forms (CRFs)	19 Feb 2019; v1.0

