11.1 Adverse events

Adverse events (AE) will be coded using MedDRA, and the National Cancer Institute Common Terminology Criteria for AEs (CTCAE criteria v5.0 or higher). They will be presented by primary System Organ Class (SOC) and Preferred Term (PT), or by PT only (in descending order) by dose cohort and overall. Subjects will be summarized at most one time per SOC and at most one time per PT, unless otherwise specified.

Adverse events are collected from the first GEN3009 dose until 30 days after the last GEN3009 dose. Treatment-emergent adverse events (TEAEs) are defined as AEs which begin, or worsen, during the on-treatment period ending 4 weeks after the last dose of trial medication as defined in Section 5.4. Adverse events collected during the post-treatment period will be flagged in data listings, and excluded from summaries, and will not be categorized as TEAEs.

The following summaries of TEAEs will be presented:

- All TEAEs, by SOC and PT
- All TEAEs, by PT, in order of descending frequency
- Serious TEAEs adverse events (SAEs), by SOC and PT
- Non-serious TEAEs, by SOC and PT
- TEAEs of CTCAE grade 3 or higher, by SOC and PT
- Non-serious TEAEs of CTCAE grade 3 or higher, by SOC and PT
- Related non-serious TEAEs of CTCAE grade 3 or higher, by SOC and PT
- TEAEs leading to dose reduction or dose interruption, by SOC and PT
- TEAEs leading to permanent discontinuation of trial treatment, by SOC and PT
- TEAEs by SOC, PT, and severity, where subjects are presented at the highest recorded severity level within SOC and PT
- Related TEAEs, by SOC and PT
- Related serious TEAEs, by SOC and PT
- TEAEs by SOC, PT, and relationship, where subjects are presented at the highest recorded relationship within SOC and PT

- Fatal TEAEs

The following tables will also be presented by overall ADA status, as per Section 11.8.

- Non-serious TEAEs of CTCAE grade 3 or higher, by SOC and PT
- Fatal TEAEs

All adverse events will be listed by subject, with those beginning during the post-treatment period flagged. Additional listings will be presented for all SAEs, all AEs leading to withdrawal of treatment, non-serious AEs of grade 3 or higher, and fatal AEs.

In addition, adverse events will be presented graphically by the incidence of AEs over infusion number, and using a swim lane plot to monitor the severity of AEs over time.

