The objective of the interim analysis during the Dose Expansion part is to evaluate safety data.

This analysis will be performed after 20 subjects (across the 3 diagnosis cohorts) have been exposed and followed for 2 cycles. Subjects who have been treated, but withdrawn from the study prior to the end of the second cycle, will be included.

The cut-off date for the interim analysis will be based on the 20th subject in the Dose Expansion part completing the second cycle (i.e., 8 weeks after the first dose), with additional time allowed for data entry and cleaning as necessary.

This interim analysis is performed to review safety data. No pre-specified stopping criteria will be utilized.

The interim analysis results will be presented using the FAS or Safety Set, unless otherwise specified. The following statistical summaries and listings will be presented:

- Summary of subject accounting and disposition, using the FAS, as described in Section 6
- Summary of subject demographics, using the FAS, as described in Section 7

- Summary of TEAEs by SOC and PT, using the Safety Analysis set, as described in Section 11.1
- Listing of adverse events, by subject and time point

15 Statistical Analyses for Safety Monitoring

The statistical analysis for safety monitoring is specified in a separate DMC charter.

16 Data Exchange Procedures

All analyses will be communicated to the sponsor and DMC through the use of Clinipace's Secure File Exchange (SFE) site.

17 Software

The data will be analysed using SAS version 9.3 or higher.

18 Abbreviations

AE	Adverse Event
ADA	Anti-Drug Antibodies
AESI	Adverse Event of Special Interest
ATC	Anatomical Therapeutic Class
AUC _{0-7 days}	Area under the plasma concentration time curve, from 0 to 7 days (Cycle 1 Day 1 only)
AUC _{0-∞} (AUC _{inf})	Area under the plasma concentration time curve, from time 0 extrapolated to infinity
AUC _{0-last}	Area under the plasma concentration time curve, from time 0 to the last measurable non-zero concentration
CI	Confidence Interval
C _{max}	Maximum observed concentration of GEN3009
CMV	Cytomegalovirus
CR	Complete Response or Complete Remission
CRF	Case Report Form
CRO	Contract Research Organization
CTCAE	Common Terminology Criteria for Adverse Events
DDS	Dose-Determining Analysis Set
DLBCL	Diffuse Large B-cell Lymphoma
DLT	Dose Limiting Toxicity
DMC	Data Monitoring Committee
DOR	Duration of Response
ECG	Electrocardiogram
ECOG	Eastern Cooperative Oncology Group
EFF	Response-Evaluable set

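### SAP 14.2 disclaims stopping criteria at the 20-subject Expansion safety look, although protocol 4.4.3 applies three 33% criteria there, and the look's only AE table cannot show that one is met

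*Protocol*

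**What the plan says.** **Protocol 4.4.3** (v7.0, Amendment 5) states that "the following stopping criteria are applicable to subjects who have completed the DLT period during the Dose Escalation, as well as subjects enrolled in Expansion". The three criteria are each met at 33% or more of subjects:

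- IRR of Grade 3 or higher;
- Grade 4 neutropenia that persists beyond 7 days and is not explained by the underlying disease;
- cytokine release syndrome (CRS) or ICANS of Grade 3 or higher.

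The section does not say whether the percentage is taken per cohort, per trial part or pooled.

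**SAP 14.2** plans a safety interim once 20 subjects across the three monotherapy cohorts have been followed for two cycles. It says: "No pre-specified stopping criteria will be utilized". Besides disposition and demographics, the outputs are one AE table, "Summary of TEAEs by SOC and PT, using the Safety Analysis set, as described in Section 11.1", and one listing, "Listing of adverse events, by subject and time point". SAP 11.1 defines a table of "TEAEs of CTCAE grade 3 or higher, by SOC and PT", but it is not among the interim outputs.

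**Context.** SAP 1.1 gives protocol v4.0 (Amendment 2) as its basis. SAP 15 adds: "The statistical analysis for safety monitoring is specified in a separate DMC charter". Protocol 11.10 plans no formal interim. Protocol 10.8 has the DMC review Expansion data at intervals set in its charter, and protocol section 11 allows extra analyses to support DMC meetings.

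**The concern.** A statistician who follows the SAP at the one Expansion safety look it defines would not evaluate criteria that the protocol says apply to those subjects. Someone who tried to evaluate them from the planned table could not, because every criterion needs a grade and the neutropenia criterion also needs duration and attribution.

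Neutropenia is where this matters most. Protocol 4.3.2 describes it as transient and credits G-CSF, given when Grade 3 or 4 neutropenia begins, with recovery in time for the next dose. For neutropenia of Grade 3 or higher, protocol 6.6.1 says "use of growth factors is mandated in the Dose Escalation and Safety Run-in parts of the study". In the monotherapy Expansion cohorts growth factors are left to the investigator. How long Grade 4 neutropenia lasts could therefore differ between escalation and Expansion, and the interim table does not show it.

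**Working it through.** **1. What each criterion needs and what the interim table gives**

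| Criterion (protocol 4.4.3) | Needs | In the SOC/PT table |
|---|---|---|
| Grade 3+ IRR | grade | any-grade count only |
| Grade 4 neutropenia beyond 7 days, not due to disease | grade, duration, attribution | any-grade count only |
| Grade 3+ CRS or ICANS | grade | any-grade count only; mainly concerns the combination cohort, which this look does not include |

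Even the Grade 3+ table in SAP 11.1 would not give the duration of neutropenia. The documents state no operating characteristics for the 33% limits, so there is no plan figure to reproduce.

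**2. The limit as a count**

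This is the smallest x with x/n ≥ 0.33. For n = 20, 6/20 = 30% does not meet it and 7/20 = 35% does, so the limit is 7. This assumes that the three monotherapy cohorts are pooled.

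**3. Can the table rule a crossing out?**

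Only if the any-grade count is below 7. Protocol 2.1.4.1 reports any-grade rates in the first 18 subjects: neutropenia 94.4% (17/18) and IRR 61.1% (11/18). With X ~ Binomial(20, p):

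- neutropenia, p = 17/18: P(X ≥ 7) > 0.999;
- IRR, p = 11/18: P(X ≥ 7) = 0.995;
- IRR at its lower 95% Clopper-Pearson limit, p = 0.357: P(X ≥ 7) = 0.61.

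The table will probably not rule a crossing out, and it can never confirm one.

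**4. How likely is a crossing?**

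Any-grade rates do not answer this. Protocol 7.2 counts Grade 4 neutropenia beyond 7 days, not due to disease, as a DLT. Protocol 2.1.4.1 reports no DLT in 18 evaluated subjects, so the Cycle 1 rate of the qualifying event is 0/18. The upper two-sided 95% limit is 1 − 0.025^(1/18) = 0.185, and at that rate P(X ≥ 7 of 20) = 0.061. IRRs were reported as mostly at the first infusion and of Grade 1 or 2.

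Over a range of assumed true qualifying rates:

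| True rate | 10% | 20% | 25% | 33% | 40% | 50% |
|---|---|---|---|---|---|---|
| P(X ≥ 7 of 20) | 0.002 | 0.087 | 0.214 | 0.508 | 0.750 | 0.942 |

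The 0/18 covers Cycle 1 only, at the doses tested by the June 2021 data cut, in the part where the current protocol mandates growth factors. The SAP look covers two cycles at the recommended dose, with growth factors discretionary.

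**5. The denominator**

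Protocol 4.4.3 names both escalation subjects past the DLT period and Expansion subjects. As an illustration, 7 events are 7/20 = 35% of 20 Expansion subjects, so the limit is met. If the 18 escalation subjects are added with no events, they are 7/38 = 18.4%, well under a limit of 13 (12/38 = 31.6%, 13/38 = 34.2%). Taken per cohort, 3 of 7 or 2 of 6 subjects would be enough. The reading chosen can decide the result.

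**The case against.** The strongest reply has four parts.

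- **The SAP sentence governs one look and does not suspend 4.4.3.** Expansion monitoring belongs to the DMC, and SAP 15 places its statistics in the charter, which is not among the documents. This stands. A reader might infer that the criteria go unmonitored in Expansion, but the documents do not show that. They also do not remove a SAP sentence that contradicts the protocol, and a charter would not supply the denominator missing from 4.4.3.

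- **The conflict is version lag.** The SAP follows v4.0, and the current protocol plans no formal interim. This explains the mismatch without correcting it, and no later SAP is provided. Whether v4.0 contained these limits cannot be checked, so the SAP cannot be faulted for misreading the protocol it was written to. If the look is dropped, a table of the criteria would still serve the Expansion DMC reviews.

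- **The listing probably carries what the table lacks.** SAP 5.1 puts all collected subject data into listings unless stated otherwise, and protocol 10.2 requires AE intensity and its changes to be reported. For 20 subjects a hand count is feasible. This largely stands, so the inability is confined to the table. Still, the interim listing's columns are not stated, nothing instructs the count, and the SAP says that no criteria will be used.

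- **The risk is small, and other controls exist.** Dosing is held for neutrophils below 0.5 × 10⁹/L (protocol 7.4.3.1), counts are followed to recovery (7.5.1), and IRRs have their own stopping and discontinuation rules (6.3). This stands. A reader might infer from the 94.4% any-grade rate that qualifying neutropenia could affect nearly every subject. The absence of DLTs in 18 subjects argues against that.

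**Conclusion.** The contradiction between SAP 14.2 and protocol 4.4.3 is real and should be corrected. The interim's single AE table cannot show that a limit, 7 of 20 if the monotherapy cohorts are pooled, has been reached, and at the reported any-grade rates it would seldom exclude one.

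The stakes are moderate. A neutropenia crossing looks unlikely on Cycle 1 escalation data: 0/18, and a chance of about 0.06 of reaching 7 of 20 even at the upper 95% limit of 18.5%. That reassurance assumes that escalation carries over to a setting with a longer window, possibly a higher dose and no growth-factor mandate.

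The conclusion rests on the current protocol text and on the SAP as provided. It makes no claim about the charter's content.

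**What to change.** 1. **SAP 14.2.** Replace the sentence that disclaims stopping criteria with: *The stopping criteria in protocol 4.4.3 apply and will be evaluated at this review; any criterion met is referred to the DMC and sponsor SC.*

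2. **One table.** Give n/N (%) of subjects meeting each 4.4.3 criterion, by cohort and pooled: Grade 3+ IRR; Grade 4 neutropenia beyond 7 days and not due to disease; and, for the combination cohort, Grade 3+ CRS or ICANS. Use it at the 20-subject look if that is kept, and at Expansion DMC reviews in any case.

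3. **Protocol 4.4.3.** The sponsor should state the denominator: per cohort, per part or pooled, and how escalation subjects past the DLT period enter. Limiting it to treated Expansion subjects would drop people whom the section expressly includes. That would change the rule and should not be introduced as a clarification.

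The cost is one SAP sentence, one table from data already collected, and one protocol sentence at the next amendment.
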